Alternative plausible causes, such as natural history of the underlying diseases, concomitant therapy, other risk factors, and the temporal relationship of the event to the study vaccine will be considered and investigated. The investigator will also consult the IB and/or Prescribing Information for marketed products to determine his/her assessment.

There may be situations when a SAE has occurred, and the investigator has minimal information to include in the initial report to GSK. However, it is very important that the investigator always makes an assessment of causality for every event prior to submission of the Expedited Adverse Events Report to GSK. The investigator may change his/her opinion of causality in light of follow-up information and update the SAE information accordingly. The causality assessment is one of the criteria used when determining regulatory reporting requirements.

All solicited local (injection site) reactions will be considered causally related to vaccination. Causality of all other AEs should be assessed by the investigator using the following question:

Is there a reasonable possibility that the AE may have been caused by the study vaccine?

YES : There is a reasonable possibility that the study vaccine contributed to the AE.

NO : There is no reasonable possibility that the AE is causally related to the administration of the study vaccine. There are other, more likely causes and administration of the study vaccine is not suspected to have contributed to the AE.

If an event meets the criteria to be determined as 'serious' (see Section 12.5.2), additional examinations/tests will be performed by the investigator in order to determine ALL possible contributing factors for each SAE.

Possible contributing factors include:

- Medical history.
- Other medication.
- Protocol required procedure.
- Other procedure not required by the protocol.
- Lack of efficacy of the vaccine, if applicable.
- Erroneous administration.
- Other cause (specify).

Assessment of outcomes

The investigator will assess the outcome of all unsolicited AEs (including SAEs) recorded during the study as:

- Recovered/resolved.
- Recovering/resolving.
- Not recovered/not resolved.
- Recovered with sequelae/resolved with sequelae.
- Fatal (SAEs only).

12.5.8.2.3. *Medically attended visits*

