	1	Slight or transient, 3-4 times/day, stool with abnormal properties, or slight diarrhea persisting for not more than 1 week

Adults		
Adverse Event	Intensity grade	Parameter
	2	Moderate or persistent, 5-7 times/days, stool with abnormal properties, or diarrhea >1 week
	3	>7 times/day, stool with abnormal properties, or bloody diarrhea, orthostatic hypotension, electrolyte imbalance, and requiring intravenous fluid >2 L
	4	Hypotensive shock, requiring hospitalization for treatment
Gastrointestinal symptom (Nausea)	0	Normal
	1	Transient (<24 h) or intermittent, while food intake basically normal
	2	Persistent nausea, leading to decreased food intake (24-48 h)
	3	Persistent nausea, leading to little food intake (>48 h) or require intravenous fluid infusion
	4	Life-threatening (such as hypotensive shock)
Gastrointestinal symptom (Vomiting)	0	Normal
	1	1-2 times/24 h and do not influence activities
	2	3-5 times/24 h or activities restricted
	3	>6 times within 24 h or require intravenous fluid infusion
	4	Due to hypotension, require hospitalization or nutrition by other routes
Gastrointestinal symptom (Abdominal pain)	0	Normal
	1	Mild: Gastrointestinal symptoms that are easily tolerated
	2	Moderate: Gastrointestinal symptoms that interfere with normal activity
	3	Severe: Gastrointestinal symptoms that prevent normal activity
Myalgia	0	None
	1	Mild: Myalgia that is easily tolerated
	2	Moderate: Myalgia that interferes with normal activity
	3	Severe: Myalgia that prevents normal activity

* For this study, fever is defined as temperature $\geq 37.3^{\circ}\text{C}$ as per guidelines from the Chinese authorities for axillary measurement. The preferred location for measuring temperature in this study will be the axilla.

The maximum intensity of local injection site redness/swelling will be scored at GSK using GSK's standard grading scale (based on the US Food and Drug Administration (FDA) guidelines [FDA, 2007]) and the guidelines of grading standards for AEs set by the Chinese authorities as follows.

Grade	GSK standard grading scale	Grading scale defined by Chinese authorities
0	< 20 mm diameter	Absent
1	≥ 20 mm to ≤ 50 mm diameter	25 mm to <50 mm
2	> 50 mm to ≤ 100 mm diameter	50 mm to <100 mm
3	> 100 mm diameter	≥ 100 mm
4	Not defined	Abscess, exfoliative dermatitis, and dermis or deep tissue necrosis*

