***The solicited symptom diary card doesn't allow to choose grade 4 swelling or redness. Per team agreement, the grade 4 of swelling and redness will be identified when the below Preferred Terms (from MedDRA version 25.0) are reported as unsolicited adverse events within or ongoing 7 days post each dose:**

- **Dermatitis exfoliative**
- **Necrosis**

- ***Skin necrosis***
- ***Soft tissue necrosis***
- ***Abscess***
- ***Abscess sterile***
- ***Abscess limb***
- ***Abscess soft tissue***

Fever will be graded as:

Grade	GSK standard grading scale	Grading scale defined by Chinese authorities (for axillary measurement)
0	<38.0°C	<37.3°C
1	≥38.0°C –≤38.5°C	37.3°C –<38°C
2	>38.5°C –≤39.0°C	38.0°C -<38.5°C
3	>39.0°C	38.5°C - <39.5°C
4	Not defined	≥ 39.5°C

The preferred location for measuring temperature in this study will be the axilla. If temperature is measured by other routes (such as oral or rectal), fever grading as per GSK scale will remain the same irrespective of route of measurement. For the grading scale as per Chinese authorities, the following conversion will be used:

- Axillary temperature = Oral temperature minus 0.2°C;
- Axillary temperature = Rectal temperature minus 0.5°C.
- ***Axillary temperature = Tympanic membrane temperature***
- ***For the duration of solicited adverse event within the solicited symptom follow-up or total duration, the unknown or missing end date will not be imputed.***
- The definition of HZ related complication is described in section 12.5.2 of the protocol and is presented below:-

Post-herpetic neuralgia	PHN is defined by the presence of HZ-associated severe pain persisting or appearing more than 90 days after onset of the HZ rash.
Disseminated disease	Defined as ≥ 6 HZ lesions clearly outside the primary dermatome as per the investigator's judgment.
Ophthalmic disease	Defined as HZ affecting any eye structure as per the investigator's judgment.

Neurologic disease	Defined as cranial or peripheral nerve palsies, myelitis, meningoencephalitis, stroke, etc. that is temporally associated with an episode of HZ and, in the opinion of the investigator, is caused directly by VZV infection arising from the HZ episode.
Visceral disease	Defined as an abnormality of one or more internal organs (e.g., hepatitis, pneumonitis, gastroenteritis, etc.) that is temporally associated with an episode of HZ and, in the opinion of the investigator, is caused directly by VZV infection arising from the HZ episode

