10.1.2.3.2. Studies with paper diaries

For studies using paper diaries which have questions in the CRF indicating the presence or absence of solicited events, the following rules are applicable.

- *Denominators for the summary of administration site (or systemic) solicited events will be calculated using the number of participants who respond "Yes" or "No" to at least one occurrence of the specific administration site (or systemic) solicited event. If there are at least 1 non-missing value of temperature from day 1 to day 7 post vaccination, that occurrence will be counted as well in the denominator of systemic solicited events.*
- When a specific solicited event is marked as having not occurred following a specific study dose (i.e. SDTM CE.CEOCCUR=N for the specified post-dose period for the event in question), all daily measurements will be imputed as Grade 0.

- *For fever, if there are missing values and/or non-missing values of temperature from day 1 to day 7 post vaccination which are not qualifying fever definition per protocol for GSK intensity and Chinese intensity tables, then that subject would not be considered for 'Any' rows of the solicited event summary tables.*
- When a specific solicited event is marked as having occurred following a specific study dose (i.e. SDTM CE.CEOCCUR=Y for the specified post-dose period for the event in question), any missing daily recordings will be given imputed values to allow them to contribute to the 'Any' rows but not to specific grade rows of the solicited event summary tables.
- The following table shows how participants contribute to each category for a specific solicited adverse event over the Day X to Day Y post-dose period:

Solicited adverse event category	Participants included in the calculation of the numerator
Any	All participants with at least one occurrence of the adverse event at grade 1, 2, or 3 for table by GSK intensity scale and at grade 1, 2, 3 or 4 for table by Chinese intensity scale between Day X and Day Y or with the adverse event marked as present and at least one missing daily recording between Day X and Day Y
Grade 1	All participants with at least one occurrence of the adverse event at grade 1 between Day X and Day Y
Grade 2	All participants with at least one occurrence of the adverse event at grade 2 between Day X and Day Y
At least grade 3	All participants with at least grade 3 or grade 4

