10.1.2.4. Unsolicited adverse events

Unsolicited adverse event summaries are including serious adverse events unless specified otherwise.

Missing relationship with study vaccine, and outcome of unsolicited adverse events will not be replaced and will appear as 'UNKNOWN' when displayed in a statistical output.

Missing severity will follow the next imputation rules:

- *If serious adverse event = 'Y' then severity = 'Severe'*
- *If serious adverse event = 'N' and action taken with study vaccine(s) as a result of the event = 'Dose not changed' and subject did not withdraw from the study due to this event, then severity = 'Mild'*
- *If previous two rules were not applicable, then severity = 'Moderate'*

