10.1.3.5. Counting rules for combining solicited and unsolicited adverse events

For output combining solicited and unsolicited adverse events, all serious adverse events will be considered systemic events since the administration site flag is not included in the expedited adverse event CRF pages. Unsolicited adverse events with missing administration site flag will also be considered systemic.

Multiple events with the same preferred term which start on the same day are counted as only one occurrence.

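### Chinese-scale grade 4 injection-site redness and swelling is assigned from eight Preferred Terms with no condition that the event be at the injection site

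*SAP*

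**What the plan says.** SAP section 9.2.3 introduces the redness and swelling scale as one for local reactions: "The maximum intensity of local injection site redness/swelling will be scored at GSK using GSK's standard grading scale", and also on the scale of the Chinese authorities. Grade 4 exists only on the Chinese scale and is described there by abscess, exfoliative dermatitis or tissue necrosis instead of a diameter.

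A footnote to that grade 4 cell explains that the diary card offers no way to record grade 4. Instead, "the grade 4 of swelling and redness will be identified when the below Preferred Terms" are "reported as unsolicited adverse events within or ongoing 7 days post each dose". The terms are Dermatitis exfoliative, Necrosis, Skin necrosis, Soft tissue necrosis, Abscess, Abscess sterile, Abscess limb and Abscess soft tissue. SAP section 8 lists the use of these terms as a change from the protocol.

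Other rules bear on the same events:

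- SAP section 10.1.2.3.2 counts grade 4 in the Any row of the Chinese-scale table.
- SAP section 10.1.2.4: "Unsolicited adverse event summaries are including serious adverse events unless specified otherwise".
- SAP section 10.1.3.5, for outputs that combine solicited and unsolicited events: "all serious adverse events will be considered systemic events since the administration site flag is not included in the expedited adverse event CRF pages". It adds: "Unsolicited adverse events with missing administration site flag will also be considered systemic".

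**The concern.** The scale is local, but the rule that fills its top category tests only a coded term and a time window. An event at a remote site meets the rule as easily as one at the injection site. Both study treatments are injected in the deltoid (protocol Table 11), yet Abscess limb does not say which limb, and Abscess and Necrosis name no location at all.

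Occurrence and intensity of each solicited local event is a named secondary endpoint. Grade 4 is the most severe category and the one a safety reader looks at first. If few or no true grade 4 local reactions occur, the row could consist entirely of events that have nothing to do with the injection site, and the table would not show this.

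There is also an inconsistency between tables. A serious abscess, or a non-serious one with the flag missing, is treated as systemic in the combined outputs, while this rule makes it a local reaction in the solicited table.

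**Working it through.** The plan gives no figure to reproduce here, so the check sets the rules side by side and then scales the effect.

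**Step 1: conditions in the rule (SAP 9.2.3).** There are three: the term is one of the listed ones, it is reported as an unsolicited event, and it falls within or is ongoing in the 7 days after a dose. Terms listed: 8. Terms naming the injection or administration site: 0. The administration-site flag of SAP 10.1.3.5 is not used.

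**Step 2: an invented case.** A subject marks redness and swelling as absent on the diary. On Day 4 after a dose, a leg abscess is reported and coded to Abscess limb.

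- All three conditions are met, so the event becomes grade 4. The footnote names swelling and redness together under one shared scale, so the plain reading is that both symptoms receive it.
- Grade 4 counts in Any on the Chinese scale (SAP 10.1.2.3.2), so the subject enters Any for redness and Any for swelling.
- If the event is serious, nothing in the footnote excludes it. In the combined outputs it is systemic (SAP 10.1.3.5).

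**Step 3: which combined outputs remain.** SAP section 8 drops the related and the at-least-grade-3 versions. SAP section 5.7.1 still plans the any-grade versions, so the mismatch in step 2 concerns those only.

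**Step 4: size.** Assumed denominator: the planned 3069 subjects per group, all contributing diary data. The documents give no rates for the eight terms, so the number of events x is left open. Intervals are Clopper-Pearson, the SAP's own method (section 10.1.5.1). For x = 0 the upper limit is 1 − 0.025^(1/n).

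| Events x | x/3069 | Exact 95% CI |
|---|---|---|
| 0 | 0.000% | 0.000 to 0.120% |
| 1 | 0.033% | 0.001 to 0.181% |
| 2 | 0.065% | 0.008 to 0.235% |

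With the 2762 evaluable subjects per group as denominator instead, one event is 1/2762 = 0.036% (0.001 to 0.202%), against 0 (0.000 to 0.134%) for none.

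Percentages are shown to one decimal (SAP 10.1.4.1). One event therefore prints as a count of 1 and 0.0%, and two print as 0.1%. The visible effect is the count.

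**The case against.** The best defence is context. The rule is a footnote to a cell of a scale headed as local, so local intent is plain, and the SAP discloses the rule openly as a change. Codes on the restricted list may also exclude many remote events; how events elsewhere would be coded cannot be seen from the documents. Finally, the table is descriptive and one event prints as 0.0%.

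Most of this stands as a limit on size. It does not remove the gap: a programmer works from the stated conditions, and intent in a heading is not a condition. The reference to attribution being checked case by case in SAP section 4.2 concerns elimination codes, not this rule.

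A reader might also infer more than the documents support:

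- **That the event would be displayed as vaccine-related.** The protocol does say "All solicited local (injection site) reactions will be considered causally related to vaccination". But the relationship rows in SAP section 5.7.1 are specified for general events, and the source event, as an unsolicited one, keeps the investigator's own causality assessment.
- **That the SAP leaves open which symptom is filled.** Naming swelling and redness together reads as both.
- **That the Any row is itself faulty.** It also counts a subject "or with the adverse event marked as present and at least one missing daily recording between Day X and Day Y", so a small reaction with a blank diary day is counted while one with a complete diary is not. With a day missing, however, the maximum is unknown, and counting the subject in Any but in no grade is a defensible choice. Likewise, diameters of 1 to 24 mm have no Chinese-scale grade, but the scale is attributed to the Chinese authorities, and adding a category would alter it.
- **That the grade 1 and 2 rows count every day at that grade.** The row wording allows it, but section 9.2.3 scores the maximum and section 10.1.3.6 counts one occurrence per event and period. This is a matter of wording.

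**Conclusion.** The point holds, within narrow bounds. As written, the rule would show an event elsewhere on the body as a grade 4 local reaction for both redness and swelling, and would carry it into the Chinese-scale Any rows. If that event is serious or lacks the flag, the any-grade combined outputs treat it as systemic.

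The effect is on counts in a descriptive secondary table: 0.033 percentage points per event and symptom at 3069 per group. Neither the primary efficacy analysis nor the sample size is touched. How many such events will occur, and whether they would differ between groups, cannot be stated from the documents. The importance lies in the row concerned: it may otherwise be empty, and a single event can then define it.

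The conclusion rests on the footnote being applied literally, with no further location check in a document not seen here, such as the separate list of tables and layouts (SAP section 10.2). It is limited to the Chinese-scale table, since the GSK scale defines no grade 4 for redness or swelling.

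**What to change.** Add a location condition to the footnote in SAP section 9.2.3:

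- For non-serious unsolicited events, assign grade 4 redness and swelling only when the administration-site flag is present.
- For serious events, whose expedited pages lack the flag, assign it only after a blinded review of the existing narrative confirms that the event is at the injection site.

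The cost is a sentence or two in the SAP, slight programming, and a blinded check of any serious events coded to the eight terms, all before unblinded tables are produced. No new data are collected, assuming the flag is recorded on the non-expedited pages as section 10.1.3.5 implies. One drawback is that a true local event with a missing flag would be left out of grade 4 unless the flag is queried.

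Two wording notes can go into the same edit of section 10.1.2.3.2: say that the grade rows use the subject's maximum grade, and add the line for the Chinese-scale grade 3 row that section 5.7.1 names but this section does not define. The Any rule and the Chinese scale itself should stay as they are.

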10. ANNEXES

10.1. Business rules for standard data derivations and statistical methods

This section contains standard rules for data display and derivation for clinical and epidemiological studies. These rules will be applied along with those detailed in section 9 (additional study-specific rules).

10.1.1. Attributing events to vaccine doses

The dose relative to an event is the most recent study dose given to a subject prior to the start of a given event. For example, if the start date of an adverse event is between Dose 1 and Dose 2, the relative dose will be Dose 1.

If an event starts on the same day as a study dose, the relative dose will be derived from the additional information provided in the CRF using the contents of the flag indicating if the event occurred before or after study dose. If 'after study dose' is selected, the relative dose for the event will be the one administered on the start day of the event. If 'before study dose' is selected, the relative dose for the event will be the dose prior to this one.

10.1.2. Handling of missing data

10.1.2.1. Dates

When partially completed dates (i.e. with missing day or month) are used in calculations, the following standard rules will be applied:

- A missing day will be replaced by 15
- A missing day and month will be replaced by June 30th.

The following exceptions apply:

- Adverse event start dates with missing day: If the event starts in the same month as at least one of the study doses, the contents of AE.AESTRTPT (the flag indicating if the event occurred before or after study dose) will be used to complete the date. If 'after study dose' is selected, the imputed start date will match the first (or only) study dose given during that month. If 'before study dose' is selected, the imputed date will be one day before the first (or only) study dose given during that month.
- Adverse event start dates with missing day and month: If the event starts in the same year as at least one of the study doses, the contents of AE.AESTRTPT (the flag indicating if the event occurred before or after vaccination) will be used to complete the date. If 'after vaccination' is selected, the imputed start date will match the first (or only) study dose given during that year. If 'before vaccination' is selected, the imputed date will be one day before the first (or only) study dose given during that year.
- All other cases of incomplete AE or concomitant medication/vaccination start date will follow the standard rules above.

10.1.2.2. Laboratory data

Missing laboratory results (including immunological data) will not be replaced.

10.1.2.3. Daily recording of solicited adverse events

10.1.2.3.1. Studies with electronic diaries

Not applicable for the study

10.1.2.3.2. Studies with paper diaries

For studies using paper diaries which have questions in the CRF indicating the presence or absence of solicited events, the following rules are applicable.

- *Denominators for the summary of administration site (or systemic) solicited events will be calculated using the number of participants who respond "Yes" or "No" to at least one occurrence of the specific administration site (or systemic) solicited event. If there are at least 1 non-missing value of temperature from day 1 to day 7 post vaccination, that occurrence will be counted as well in the denominator of systemic solicited events.*
- When a specific solicited event is marked as having not occurred following a specific study dose (i.e. SDTM CE.CEOCCUR=N for the specified post-dose period for the event in question), all daily measurements will be imputed as Grade 0.

- *For fever, if there are missing values and/or non-missing values of temperature from day 1 to day 7 post vaccination which are not qualifying fever definition per protocol for GSK intensity and Chinese intensity tables, then that subject would not be considered for 'Any' rows of the solicited event summary tables.*
- When a specific solicited event is marked as having occurred following a specific study dose (i.e. SDTM CE.CEOCCUR=Y for the specified post-dose period for the event in question), any missing daily recordings will be given imputed values to allow them to contribute to the 'Any' rows but not to specific grade rows of the solicited event summary tables.
- The following table shows how participants contribute to each category for a specific solicited adverse event over the Day X to Day Y post-dose period:

Solicited adverse event category	Participants included in the calculation of the numerator
Any	All participants with at least one occurrence of the adverse event at grade 1, 2, or 3 for table by GSK intensity scale and at grade 1, 2, 3 or 4 for table by Chinese intensity scale between Day X and Day Y or with the adverse event marked as present and at least one missing daily recording between Day X and Day Y
Grade 1	All participants with at least one occurrence of the adverse event at grade 1 between Day X and Day Y
Grade 2	All participants with at least one occurrence of the adverse event at grade 2 between Day X and Day Y
At least grade 3	All participants with at least grade 3 or grade 4
Grade 4*	All participants with at least one occurrence of the adverse event at grade 4 between Day X and Day Y

*this is specific to the study as grade 4 has also been defined for some solicited adverse event collected in the study as per Chinese regulation.

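### The solicited-fever rules let a participant with no recorded temperature count as fever-free, and they conflict when fever is marked present but temperatures are missing

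*SAP*

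**What the plan says.** All the rules are in SAP 10.1.2.3.2 (Studies with paper diaries).

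- **Denominator.** It is "calculated using the number of participants who respond 'Yes' or 'No' to at least one occurrence of the specific administration site (or systemic) solicited event". With at least one non-missing Day 1-7 temperature, "that occurrence will be counted as well in the denominator of systemic solicited events".
- **Fever.** The condition is "if there are missing values and/or non-missing values of temperature from day 1 to day 7 post vaccination which are not qualifying fever definition" and the consequence is "then that subject would not be considered for 'Any' rows of the solicited event summary tables".
- **Event marked as not having occurred (CEOCCUR=N).** Every day is set to Grade 0.
- **Event marked as having occurred (CEOCCUR=Y).** The rule opens "When a specific solicited event is marked as having occurred following a specific study dose" and continues "any missing daily recordings will be given imputed values to allow them to contribute to the 'Any' rows", without adding to any specific grade.
- **Category table, Any row.** Besides participants with a graded occurrence, it takes those "with the adverse event marked as present and at least one missing daily recording between Day X and Day Y". Neither this row nor the CEOCCUR=Y rule makes an exception for fever.

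Three other places matter. SAP 5.7.1 tabulates fever with exact 95% CIs on two scales, with Any starting at 38.0°C on the GSK scale and 37.3°C on the Chinese scale. SAP 4.1.2 limits the solicited-event set to participants who completed and returned the diary card. SAP 6 makes all secondary analyses descriptive.

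**The concern.** There are two separate problems.

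First, the denominator does not require that fever was ever measured, while the fever rule sends an unmeasured participant to the non-event side. An unknown outcome is reported as no fever. That can lower the fever percentage or leave it unchanged; it cannot raise it. The exact CI is also computed on an N that includes people who contribute no information about fever.

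Second, for a participant who marks fever as present but has blank temperatures, the fever rule and the general rule give opposite answers, and the SAP does not say which governs. Two programmers could follow the text faithfully and produce different fever tables.

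Fever is one of the solicited general events under the secondary safety objective, so its numerator and denominator should be unambiguous even though no hypothesis test depends on them.

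**Working it through.** The plan states no fever rate and no share of missing temperatures, so there is no figure of its own to reproduce. The check is a case-by-case reading followed by a dilution formula with assumed inputs.

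**Case reading, with one denominator shared by all systemic events**

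1. No temperature, at least one systemic Yes/No answer: in the denominator, not in Any fever.
2. No temperature and no systemic answer: not in the denominator.
3. Another symptom marked Yes, some days blank: in Any.
4. Another symptom marked No, some days blank: Grade 0, not in Any.
5. Another symptom left blank, some other systemic item answered: in the denominator, not in Any. This is the same treatment as case 1.
6. Fever marked Yes, temperatures missing: out of Any by the fever rule, in Any by the CEOCCUR=Y rule and by the category table.

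Only case 6 treats fever differently from other symptoms. It also arises with partial data. Suppose fever is marked Yes, Day 1 reads 37.8°C, Day 2 is blank, and no other reading is higher. On the Chinese scale the participant is in Any under every rule, because 37.8 is at or above 37.3. On the GSK scale, where 37.8 is below 38.0, the category table puts the participant in Any and the fever rule takes the participant out.

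**Size of the effect in case 1**

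Let p be the fever rate among participants with a temperature and m the share of the systemic denominator with none on Days 1-7. If temperatures are missing at random, reported rate = p × (1 − m), so the relative shortfall is m. Both p and m are assumptions.

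| Assumed p | m = 1% | m = 5% | m = 10% |
|---|---|---|---|
| 5% | 4.95% | 4.75% | 4.50% |
| 20% | 19.8% | 19.0% | 18.0% |
| 30% | 29.7% | 28.5% | 27.0% |

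With the planned 3069 per group as an upper bound for the denominator, m = 1% is about 31 participants and m = 5% about 153.

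With the same m in both groups, a between-group difference d becomes d × (1 − m). For an assumed 20% against 3%, 17.0 points becomes 17.0 × 0.98 = 16.7 at m = 2% and 17.0 × 0.95 = 16.2 at m = 5%.

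For scale, the approximate 95% CI half-width at 20% is 1.96 × √(0.2 × 0.8 / 3069) = 1.4 points. The shortfall 20 × m reaches 1.4 points at m = 7%.

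**The case against.** The strongest reply is that the denominator wording refers to the specific event and so permits an event-specific denominator. The temperature sentence would then supply fever's equivalent of a Yes/No answer, since SAP Table 3 grades the other systemic symptoms but records temperature as a value in °C. On that reading a participant with no temperature and no fever answer leaves the fever denominator, and there is no dilution from that source. This reading is possible. The shared reading fits better, because the temperature sentence adds the participant to the denominator of systemic events as a class. Even on the event-specific reading, a fever item answered No with no temperature becomes Grade 0 and counts as fever-free.

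On the conflict, the fever rule can be read as a deliberate exception. There is a good reason for one: a sub-threshold reading plus a blank day should not place someone in a row defined as 38.0°C or above. That reasoning is sound and the fix adopts it, but the SAP does not state the precedence. The conflict also presumes that the CRF has a fever Yes/No item. The section's opening sentence suggests this, but the documents do not confirm it.

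On size, m requires every Day 1-7 temperature to be missing on a completed, returned card. Protocol 12.5.3 instructs participants to record an evening temperature, and Protocol 12.5.8 has cards verified with them. A small m is therefore likely. If those who skipped the thermometer tended to feel well, the rate among measured participants would itself be too high. Both points stand.

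A reader might infer two stronger claims. One is that missing days count toward Any for every symptom except fever. They do not: they count only when the symptom is marked present, and a blank item is a non-event for any symptom. The other is that the bias exceeds the stated precision. That needs m of about 7% at a 20% rate, and nothing in the documents supports such a figure.

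**Conclusion.** The concern holds in limited form. On the more natural reading of SAP 10.1.2.3.2, a participant who answered another systemic item but has no Day 1-7 temperature is counted as not having fever. The fever percentage is therefore at or below the rate among measured participants, by a relative amount m under missingness at random. At an assumed 20% rate that is 0.2 points for m = 1% and 1.0 point for m = 5%. Neither the rate nor m is in the documents, and m is probably small.

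The inconsistency between rules is confined to fever marked present with some or all temperatures missing. It needs no assumed missing rate, only that the CRF asks a fever Yes/No question.

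The documents do not support reading this as a threat to the trial's conclusions. It affects descriptive reactogenicity tables and leaves the primary efficacy conclusion untouched. It is a tabulation rule and has no bearing on clinical management.

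**What to change.** In SAP 10.1.2.3.2:

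- Set the denominator of the fever rows to participants with at least one recorded temperature on Days 1-7 after that dose, and show that N beside the rows.
- State that the fever rule takes precedence over the CEOCCUR=Y rule and the Any row of the category table, so that Any fever on each scale requires a recorded temperature at or above that scale's threshold.
- Report, by group and dose, the number with no temperature and the number with fever marked present but no temperature.

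This keeps numerator and denominator consistent: a participant with fever marked present and no temperature at all is in neither and appears in the separate count. A participant with only sub-threshold readings and some blank days remains a non-event, so fever on an unmeasured day can still be missed.

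The cost is a few sentences of SAP text, one extra N per fever row and the two counts. The fever percentage will be slightly higher.
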